*** Subject Population (h-m) ***

8. Subject Population (Input N/A if not applicable)

h) Inclusion and Exclusion Criteria (e.g., Participants must have 20/20 vision, Participants must be 30-45 years of age, etc.)

Identify inclusion criteria.

For inclusion in the study subjects should fulfill the following criteria:

1. Provision of informed consent prior to any study specific procedures.
2. Aged 18-50 years.
3. No known Type 2 Diabetes
4. Body mass index 25-45 kg/m², inclusive
5. Sedentary (maximum of 2/week regularly scheduled activity sessions of < 20 minutes during the previous 2 years)
6. Completion of a screening visit consisting of medical history, physical examination, and 12-lead electrocardiogram and blood pressure assessment at rest and during incremental exercise to volitional exhaustion (Note: Subjects with abnormal screening values may be eligible if the results are not clinically significant, as judged by the investigator or medical monitor)
7. Agree to abide by the study schedule and dietary restrictions and to return for the required assessments
8. Be willing and able to repeatedly perform exercise
9. Women of childbearing potential must have negative pregnancy test and be using acceptable contraception

Identify exclusion criteria.

Subjects should not enter the study if any of the following exclusion criteria are fulfilled:

1. Evidence of clinically significant cardiovascular, respiratory, renal, hepatic, pulmonary, gastrointestinal, haematological, neurological, psychiatric, or other disease that may interfere with the objectives of the study or the safety of the subject, as judged by the investigator in agreement with the sponsor or medical monitor, have been hospitalized in the past 2 years as a result of these conditions, or are receiving pharmacological treatment for these conditions.
2. Use of prescription drugs (see exceptions listed below) or herbal preparations in the 2 weeks before study commencement.

PPermitted Prescription Drugs

- Birth Control
- Less than 7 days, short course antibiotics. Note: Rifampin is not permitted.

Protocol Title: Does Dapagliflozin Augment The Favorable Adaptation To Endurance Exercise Training?
Clinical Research Protocol Title: Dapagliflozin Augments The Favorable Adaptation To Endurance Exercise Training

Protocol Type: Biomedical

Date Submitted: 11/01/2018

Approval Period: 11/06/2018-11/05/2019

Important Note: This Print View may not reflect all comments and contingencies for approval. Please check the comments section of the online protocol. Questions that appear to not have been answered may not have been required for this submission. Please see the system application for more details.

- Less than 7 days, short course antibiotics. Note: Rifampin is not permitted.
- Other medicines, for GERD, depression, seasonal allergies and OTC analgesics, may be allowed, but will be approved on a case-by-case basis.
- 3. Is currently enrolled in another clinical study for another investigational drug or has taken any other investigational drug within 30 days before the screening visit.
- 4. Habitual and/or recent use (within 2 years) of tobacco.
- 5. Being considered unsuitable for participation in this trial for any reason, as judged by the investigator or medical monitor.
- 6. History of serious hypersensitivity reaction to Dapagliflozin.
- 7. Severe renal impairment, end-stage renal disease, or dialysis.
- 8. Pregnant or breastfeeding patients.
- 9. Severe hepatic insufficiency and/or significant abnormal liver function defined as aspartate aminotransferase (AST) >3x upper limit of normal and/or alanine aminotransferase (ALT) >3x upper limit of normal.
- 10. Total bilirubin >2.0 mg/dL (34.2 umol/L).
- 11. Positive serologic evidence of current infectious liver disease including Hepatitis B viral antibody IGM, Hepatitis B surface antigen and Hepatitis C virus antibody.
- 12. Estimated Glomerular Filtration Rate <60 mL/min/1.73 m² (calculated by Cockcroft-Gault formula).
- 13. History of bladder cancer.
- 14. Recent cardiovascular events in a patient, including any of the following: acute coronary syndrome within 2 months prior to enrolment; hospitalization for unstable angina or acute myocardial infarction within 2 months prior to enrolment; acute stroke or trans-ischemic attack within two months prior to enrolment; less than two months post coronary artery revascularization; congestive heart failure defined as New York Heart Association class IV, unstable or acute congestive heart failure. Note: eligible patients with congestive heart failure, especially those who are on diuretic therapy, should have careful monitoring of their volume status throughout the study.
- 15. Blood pressure at enrolment: Systolic blood pressure ≥165 mmHg and/or diastolic blood pressure ≥100 mmHg.
- 16. Blood pressure at randomization: Systolic blood pressure ≥165 mmHg and/or diastolic blood pressure ≥100 mmHg
- 17. Patients who, in the judgment of the medical monitor, may be at risk for dehydration.

i) **Describe your screening procedures. Attach your screening document(s) (e.g., health history questionnaire) in the Attachment Section (#16).**

Please see attached screening document. Subjects will be provided with the option of receiving an electronic version of the screening document in advance of visit 1.

j) **Describe how you will be cognizant of other protocols in which subjects might be participating. Please explain if subjects will be participating in more than one study.**

Subjects will be asked if they are participating in another study or if they intend to enroll in another study. Subjects will be permitted to participate in other studies when participation does not interfere with the current study - that is, no possible interaction with Dapagliflozin or exercise, no increase risk to subject safety, etc.

Protocol Title: Does Dapagliflozin Augment The Favorable Adaptation To Endurance Exercise Training?
Clinical Research Protocol Title: Dapagliflozin Augments The Favorable Adaptation To Endurance Exercise Training

Protocol Type: Biomedical

Date Submitted: 11/01/2018

Approval Period: 11/06/2018-11/05/2019

Important Note: This Print View may not reflect all comments and contingencies for approval. Please check the comments section of the online protocol.
Questions that appear to not have been answered may not have been required for this submission.
Please see the system application for more details.

k) Compensation. Explain the amount and schedule of compensation, if any, that will be paid for participation in the study. Compensation includes food, gift cards, money, tokens, etc. Include provisions for prorating payment, if applicable. Compensation should be prorated if several activities are involved for different time periods (e.g., \$10 for session #1, and \$10 for session #2).

Subjects are provided with the following information: "If you complete all 51 of the visits, and all of the procedures as described, you may receive \$300 in total. This payment will be paid in installments and prorated as follows: you will not receive compensation for visit 1 (the screening visit). You will receive \$80 on completion of visits 2, 3 and 4. You will not receive compensation for visits 5-48; nor will you be charged for this supervised exercise training. You will receive \$60 for completion of visit 49. You will receive \$60 for completion of visit 50. You will receive \$60 for completion of visit 51. If you attend 100% of your scheduled visits, and arrive no later than 10 minutes after the scheduled appointment time for all appointments, you will receive a bonus of \$40."

l) Costs. Please explain any costs that will be charged to the subject.

Subjects are provided with the following information: "Other than transport to and from the lab, your participation should incur no costs. You will not be charged for your supervised exercise training." The commercial cost for 12-weeks of supervised exercise training is approximately \$1,200.

m) Estimate the probable duration of the entire study. This estimate should include the total time each subject is to be involved and the duration the data about the subject is to be collected (e.g., This is a 2-year study. Participants will be interviewed 3 times per year; each interview will last approximately 2 hours. Total approximate time commitment for participants is 12 hours). These times should be consistent with the time commitment listed on the consent document.

The study will take place over approximately 2 years. Subjects will be involved for approximately 4 months and will be asked to visit the Human Performance Clinical Research Laboratory on 52 different days. Visits will last between 30 minutes and 3 hours.

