c. **Please summarize any protocol deviations/violations or unanticipated problems (UPs)/adverse events (AEs) since the last continuing review or original approval (if this is your first continuing review). Please indicate if any of the unanticipated problems/events are being reported to the IRB for the first time. If you have or will make changes to your protocol as a result of any unanticipated problem/event or adverse event, please summarize those changes in Question #5 below.**

Please see AE log. No deviation occurred since the last approval period.

e. **Complaints about the research during the last year.**

none

3. **A summary of any recent findings, literature, or other relevant information (especially pertaining to risks), if applicable.**

none

4. **Description of the remainder of project:**

N Do you plan to recruit more subjects?

Y If "No," have all subjects completed all research-related interventions? Note: Protocols must be renewed to continue recruiting participants and/or collect data from already recruited participants.

Y Are you only performing data analysis? NOTE: If you are analyzing data with no identifiers (i.e., you cannot link your data to individuals), you can close your protocol by submitting a Final Report.

N Does this protocol have a Data Safety Monitoring Board (DSMB)?

If you do have a DSMB, have reports been submitted to the IRB and/or the Sponsor? Upload any DSMB reports that have not yet been submitted to the IRB since the approval or last continuing review.

5. **Summarize all approved changes in the protocol since the last continuing review or since the original approval (if this is your first continuing review). For example: Have you amended your protocol during the past year? Are you requesting to make any changes for the upcoming year? Have you**

Protocol Title: Does Dapagliflozin Augment The Favorable Adaptation To Endurance Exercise Training?
 Clinical Research Protocol Title: Dapagliflozin Augments The Favorable Adaptation To Endurance Exercise Training

Protocol Type: Biomedical

Date Submitted: 11/01/2018

Approval Period: 11/06/2018-11/05/2019

Important Note: This Print View may not reflect all comments and contingencies for approval. Please check the comments section of the online protocol. Questions that appear to not have been answered may not have been required for this submission. Please see the system application for more details.

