Document Name	SGLT2 Inhibitors Diabetes
Document Type	Other Protocol Material
Attachment	SGLT2 Inhibitors New Diabetes Drug
Document Name	SGLT2 Inhibitors New Diabetes Drug
Document Type	SOP
Attachment	HP-03-R1 Reporting AEs SOP
Document Name	HP-03-R1 Reporting AEs SOP
Document Type	Recruitment Material (e.g., flyers, email text, verbal scripts)
Attachment	14-5529H Recruitment Examples 02062015
Document Name	14-5529H Recruitment Examples 02062015
Document Type	Other Protocol Material
Attachment	Id cards for subjects
Document Name	Id cards for subjects
Document Type	Sponsor's Protocol
Attachment	Protocol ISSDAP0010-02062015
Document Name	Protocol ISSDAP0010-02062015
Document Type	Other Protocol Material
Attachment	FDA-1572_508(7.13)_05June2015
Document Name	FDA-1572_508(7.13)_05June2015

Protocol Title: Does Dapagliflozin Augment The Favorable Adaptation To Endurance Exercise Training?
Clinical Research Protocol Title: Dapagliflozin Augments The Favorable Adaptation To Endurance Exercise Training

Protocol Type: Biomedical

Date Submitted: 11/01/2018

Approval Period: 11/06/2018-11/05/2019

Important Note: This Print View may not reflect all comments and contingencies for approval. Please check the comments section of the online protocol.
Questions that appear to not have been answered may not have been required for this submission.
Please see the system application for more details.

Document Type**Sponsor's Protocol****Attachment**

[name] 0010 IISR FINAL

Document Name

[name] 0010 IISR FINAL

Document Type**Other Protocol Material****Attachment**

Important Communication from AZ regarding DKA other T2D studies 3 July 2015

Document Name

Important Communication from AZ regarding DKA other T2D studies 3 July 2015

Document Type**Other Protocol Material****Attachment**

AZ Email 07072015

Document Name

AZ Email 07072015

Document Type**Questionnaire/Survey****Attachment**

Screening Med History 08262015

Document Name

Screening Med History 08262015

Document Type**Other Protocol Material****Attachment**

FDA safety warning 04Dec2015

Document Name

FDA safety warning 04Dec2015

Document Type**Other Protocol Material****Attachment**

CDC Hepatitis B Fact Sheet

Document Name

CDC Hepatitis B Fact Sheet

Document Type**Recruitment Material (e.g., flyers, email text, verbal scripts)****Attachment**

Recruitment_AZ_Exercise

Document Name

Recruitment_AZ_Exercise

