*** Obligations ***

Obligations (Researcher's Responsibilities)

The Principal Investigator is ultimately responsible for the conduct of the project. Obligations of the Principal Investigator are:

Conduct the research involving human subjects as presented in the protocol, including modifications, as approved by the Department and Institutional Review Board. Changes in any aspect of the study (for example project design, procedures, consent forms, advertising materials, additional key personnel or subject populations) will be submitted to the IRB for approval before instituting the changes (PI will submit the "Amendment/Revision" form);

Provide all subjects a copy of the signed consent form, if applicable. Investigators will be required to retain signed consent documents for three (3) years after close of the study;

Protocol Title: Does Dapagliflozin Augment The Favorable Adaptation To Endurance Exercise Training?
Clinical Research Protocol Title: Dapagliflozin Augments The Favorable Adaptation To Endurance Exercise Training

Protocol Type: Biomedical

Date Submitted: 11/01/2018

Approval Period: 11/06/2018-11/05/2019

Important Note: This Print View may not reflect all comments and contingencies for approval. Please check the comments section of the online protocol.
Questions that appear to not have been answered may not have been required for this submission.
Please see the system application for more details.

Maintain an approved status for Human Subjects Protection training. Training must be updated every three (3) years (Contact RICRO to check your current approval/renewal dates). For more information: Human Subjects Training Completed?

Submit either the "Protocol Deviation Form" or the "Report Form" to report protocol Deviations/Violations, Unanticipated Problems (UPs) and/or Adverse Events (AEs) that occur in the course of the protocol. Any of these events must be reported to the IRB as soon as possible, but not later than five (5) working days. Note that if an event resulted in life threatening injury or death OR an event resulted in substantive harm to the safety, rights or welfare to human subjects, this must be reported to the IRB within 24 hours;

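### Does exclusion 12 need correcting because its limit is per 1.73 m² while Cockcroft-Gault returns unindexed mL/min?

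*Combined protocol and SAP*

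**What the plan says.** Item 8h of the combined protocol and SAP (Subject Population (h-m)) lists as exclusion 12: "Estimated Glomerular Filtration Rate <60 mL/min/1.73 m² (calculated by Cockcroft-Gault formula". Inclusion 4 in the same item admits BMI 25 to 45 kg/m², and inclusion 2 admits ages 18 to 50. Two other exclusions touch the kidney. Exclusion 1 bars clinically significant renal disease as judged by the investigator, and also bars recent hospital admission or drug treatment for it. Exclusion 7 bars severe impairment, end-stage disease and dialysis. Neither gives a number.

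On screening methods, item 8i says "Please see attached screening document". The Attachments section lists "Screening Med History 08262015" and, as a sponsor's protocol, "Protocol ISSDAP0010-02062015", followed by a second sponsor's protocol. None of these was supplied. A note repeated through the form warns: "This Print View may not reflect all comments and contingencies for approval". The description of screening bloods under Visit 1 names glucose, two liver enzymes and bilirubin as examples. It does not mention creatinine, but the list is not presented as complete.

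The Continuing review section, item 4, records that no more recruitment is planned and that all interventions are complete. It answers yes to the data-analysis question: "Y Are you only performing data analysis".

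**The concern.** In its standard form, Cockcroft-Gault gives creatinine clearance in mL/min. A limit per 1.73 m² needs that result multiplied by 1.73 and divided by body surface area, and the form does not mention this step. In a lean population near 1.73 m² the omission would hardly matter. Here most eligible body sizes lie above 1.73 m², so comparing a raw result with 60 would let in people whose scaled value is well under 60.

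Exclusion 12 is also the only renal criterion with a numeric limit. The Obligations section binds the investigator to "Conduct the research involving human subjects as presented in the protocol" and requires a form "to report protocol Deviations/Violations, Unanticipated Problems (UPs) and/or Adverse Events (AEs) that occur in the course of the protocol". Anyone enrolled below the stated limit would be a deviation. The form's statement that none occurred covers only the last approval period, in which nobody was studied. It says nothing about the 57 people studied before then.

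**Working it through.** **Inputs.** From the documents: limit 60 mL/min/1.73 m², BMI 25-45, age 18-50. Assumed, because the documents do not give them: the standard Cockcroft-Gault form, heights of 155 to 185 cm, actual body weight, and Mosteller surface area with Du Bois as a check. The plan has no computed figure to reproduce.

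**Formulas.**
- Cockcroft-Gault (mL/min) = (140 − age) × weight / (72 × creatinine), × 0.85 for women.
- Scaled value = raw value × 1.73 / BSA.
- Weight = BMI × (height in m)². Mosteller BSA = √(height in cm × weight / 3600). Du Bois BSA = 0.007184 × height^0.725 × weight^0.425.

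**Step 1: size of the effect if a raw value was compared with 60.** The effective scaled limit would be 60 × 1.73 / BSA. Where BSA exceeds 1.73 m², the raw values on which the two readings disagree run from 60 up to 60 × BSA / 1.73. Example at 170 cm and BMI 35: weight 35 × 1.70² = 101.1 kg; BSA √(170 × 101.1 / 3600) = 2.19; limit 103.8 / 2.19, about 47.5 unrounded; upper end 60 × 2.19 / 1.73, about 75.8 unrounded.

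| 170 cm, BMI | Weight (kg) | BSA | Effective limit (Mosteller) | Upper end of raw range | Effective limit (Du Bois) |
|---|---|---|---|---|---|
| 25 | 72.2 | 1.85 | 56.2 | 64.1 | 56.6 |
| 30 | 86.7 | 2.02 | 51.3 | 70.2 | 52.4 |
| 35 | 101.1 | 2.19 | 47.5 | 75.8 | 49.1 |
| 45 | 130.0 | 2.48 | 41.9 | 85.9 | 44.1 |

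At the corners of the assumed range the effective limit is 64.5 (155 cm, BMI 25, BSA 1.61) and 36.9 (185 cm, BMI 45, BSA 2.81). The direction reverses for the smallest participants: with BSA below 1.73, raw use is the stricter reading.

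**Step 2: size of the effect if the value was scaled.** There is no unit discrepancy. What remains unstated is the surface-area formula and the weight. The formula moves the result by a ratio of 2.48 / 2.35 = 1.06 at 170 cm and BMI 45. Weight enters in proportion, so that choice could matter more, but a weight below the actual one lowers the result and makes the criterion stricter.

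**Step 3: who could be affected under raw use.** Convert the raw range to creatinine. For a man aged 50 at 170 cm, a raw value of 60 needs creatinine 90 × weight / (72 × 60), and a scaled value of 60 needs that figure × 1.73 / BSA. At BMI 45: 90 × 130.0 / 4320 = 2.71, and 2.71 × 1.73 / 2.48 = 1.89. With unrounded weights, in mg/dL:

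| BMI | Man aged 50 | Woman aged 50 (× 0.85) |
|---|---|---|
| 25 | 1.41-1.51 | 1.20-1.28 |
| 30 | 1.54-1.81 | 1.31-1.54 |
| 35 | 1.67-2.11 | 1.42-1.79 |
| 45 | 1.89-2.71 | 1.61-2.30 |

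At age 30 each value is 110 / 90 = 1.22 times as high. The widest gaps in Step 1 therefore need clearly raised creatinine.

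**Step 4: what depends on the value.** The dependent variables in the study overview are aerobic capacity, substrate use in exercise, muscle enzyme activity, body composition, and glucose and insulin measures. Methods of statistical analyses specifies a two-way analysis of variance by time and treatment. Neither uses renal function.

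**The case for a change.** The best argument for acting is that the remedy is cheap. The mismatch is visible on the page. The judgement-based exclusions do not replace a numeric limit, and with data analysis still open a check would cover at most 57 records. A reader who wants to know which population was enrolled cannot tell from this form how the limit was applied.

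The mismatch and the silence on method both stand. The step from there to a defect does not. It needs three things in sequence, none of them documented: that staff ignored the printed unit, that someone fell in the discordant range, and that this went unreported. Anyone in that range would also have had to pass the investigator's judgement on renal disease (exclusion 1) and on general suitability (exclusion 5). Those checks are not numeric, but they bear hardest where the computed gap is widest.

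The record check has its own weakness. Listing raw values from 60 up to 60 × BSA / 1.73 finds nothing when BSA is below 1.73 m², so it would miss anyone wrongly turned away. It also needs stored creatinine, which the form does not name. Nor can a step be called absent from the plan when the screening document and both sponsor's protocols are attached but were not supplied.

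**Conclusion.** No change to the plan follows. Exclusion 12 pairs a surface-area-scaled unit with a formula that does not scale, and the form leaves the scaling step and body weight unstated. Read by its own unit, the criterion is coherent. The effective limits of about 56 to 42 mL/min/1.73 m² at 170 cm apply only under an undocumented misapplication, and they rest on assumed height, actual weight and a chosen surface-area formula. The documents contain no renal data and do not show that anyone was wrongly enrolled or excluded.

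With enrolment and treatment finished, rewording the criterion would alter no participant's status and no trial result. When the report describes eligibility, its authors can reconcile the unit with the formula in one sentence: whether the value was scaled, and with which weight and surface-area formula. That is ordinary reporting practice. I take no view on which cut-off, equation or weight is right.

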*** Risks ***

9. Risks (Input N/A if not applicable)

US Department of Health & Human Services (HHS) Regulations define a subject at risk as follows: "...any individual who may be exposed to the possibility of injury, including physical, psychological, or social injury, as a consequence of participation as a subject in any research, development, or related activity which departs from the application of those accepted methods necessary to meet his needs, or which increases the ordinary risks of daily life, including the recognized risks inherent in a chosen occupation or field of service."

Protocol Title: Does Dapagliflozin Augment The Favorable Adaptation To Endurance Exercise Training?
Clinical Research Protocol Title: Dapagliflozin Augments The Favorable Adaptation To Endurance Exercise Training

Protocol Type: Biomedical

Date Submitted: 11/01/2018

Approval Period: 11/06/2018-11/05/2019

Important Note: This Print View may not reflect all comments and contingencies for approval. Please check the comments section of the online protocol.
Questions that appear to not have been answered may not have been required for this submission.
Please see the system application for more details.

a) PI's evaluation of the overall level of Risk. (Please check one: minimal or > minimal.)

Minimal (everyday living)

Y > Minimal (greater than everyday living)

b)

For the following categories include a scientific estimate of the frequency, severity, and reversibility of potential risks. Wherever possible, include statistical incidence of complications and the mortality rate of proposed procedures. Where there has been insufficient time to accumulate significant data ON risk, a statement to this effect should be included. (In describing these risks in the consent form to the subject, it is helpful to use comparisons which are meaningful to persons unfamiliar with medical terminology.) Address any risks related to:

1. Use of investigational devices. Please include the clinical adverse events (AEs) associated with each of the devices with an indication of frequency, severity and reversibility. This information can often be found in the Investigator(s) brochure.

N/A

- 2 Use of investigational drugs. Please include the clinical AEs associated with each of the drugs with an indication of frequency, severity and reversibility. This information can often be found in the Investigator(s) brochure.

N/A

- 3 Use of commercially available drugs, reagents or chemicals. Please include the clinical AEs associated with each of the drugs with an indication of frequency, severity and reversibility. This information can often be found in the package insert provided by the manufacturer.

Please see the package insert provided by the manufacturer for further information.

Adverse reactions in placebo-controlled studies reported in more than 2% but less than 8.5 % of patients treated with Dapagliflozin include:

- Female genital mycotic infections, such as (listed in order of frequency reported): vulvovaginal mycotic infection, vaginal infection, vulvovaginal candidiasis, vulvovaginitis, genital infection, genital candidiasis, fungal genital infection, vulvitis, genitourinary tract infection, vulval abscess, and vaginitis bacterial.
- Nasopharyngitis (cold-like symptoms)

Protocol Title: Does Dapagliflozin Augment The Favorable Adaptation To Endurance Exercise Training?
Clinical Research Protocol Title: Dapagliflozin Augments The Favorable Adaptation To Endurance Exercise Training

Protocol Type: Biomedical

Date Submitted: 11/01/2018

Approval Period: 11/06/2018-11/05/2019

Important Note: This Print View may not reflect all comments and contingencies for approval. Please check the comments section of the online protocol. Questions that appear to not have been answered may not have been required for this submission. Please see the system application for more details.

•Urinary tract infections, such as (listed in order of frequency reported): urinary tract infection, cystitis, Escherichia urinary tract infection, genitourinary tract infection, pyelonephritis, trigonitis, urethritis, kidney infection, and prostatitis.

- Back pain
- Increased urination
- Male genital mycotic infections, such as (listed in order of frequency reported): balanitis, fungal genital infection, balanitis candida, genital candidiasis, genital infection male, penile infection, balanoposthitis, balanoposthitis infective, genital infection, and posthitis.
- Influenza
- Nausea
- Dyslipidemia
- Constipation
- Discomfort with urination
- Pain in extremity

In addition, use of Dapagliflozin is also associated with a risk of weight loss (up to 10 lbs over 12 weeks).

4 When performing procedures, please include all investigational, non-investigational and non-invasive procedures (e.g., surgery, blood draws, treadmill tests).

Subjects are provided with the following information pertaining to risks:

Body Composition

The risks associated with the DEXA are very low. The maximum radiation dose you will receive in this study is less than 1/1000th of the federal and state occupational whole body dose limit allowed to radiation workers (5,000 mrem). Put another way, the maximum dose from any scan we utilize with this DEXA ranges from 1.2 mrem (Whole body scan) to 12.2 mrem (for several of the regional scans, such as lumbar, femur, and forearm scans). The average annual background radiation you already receive is at least 620 mrem/year. The more radiation you receive over the course of your life, the more the risk increases of developing a fatal cancer or inducing changes in genes. The radiation in this scan is not expected to significantly increase these risks, but the exact increase in such risks is not known. There are no discomforts associated with this procedure. Women who are or could be pregnant should receive no unnecessary radiation and should not participate in this study.

Exercise Tests and Exercise Training

There is a very small chance of an irregular heartbeat during exercise (< 1% of all subjects).

Protocol Title: Does Dapagliflozin Augment The Favorable Adaptation To Endurance Exercise Training?
Clinical Research Protocol Title: Dapagliflozin Augments The Favorable Adaptation To Endurance Exercise Training

Protocol Type: Biomedical

Date Submitted: 11/01/2018

Approval Period: 11/06/2018-11/05/2019

Important Note: This Print View may not reflect all comments and contingencies for approval. Please check the comments section of the online protocol. Questions that appear to not have been answered may not have been required for this submission. Please see the system application for more details.

Other rare risks of a stress test are heart attack (< 5 in 10,000) and death (<2 in 10,000). Wearing a mouthpiece and nose-clip can sometimes cause dryness in the mouth and mild discomfort. Difficult exercise may make you feel very tired, light headed and nauseous. Exhausting exercise will, by definition, make you feel very tired. After any exercise your muscles might ache.

Blood Collection

When the needle goes into a vein, it may hurt for a short period of time (a few seconds). Also there may be minor discomfort of having the needle/plastic tube taped to your arm. In about 1 in 10 cases, a small amount of bleeding will occur under the skin that will cause a bruise. The risk of forming a blood clot in the vein is about 1 in 100, and the risk of significant blood loss is 1 in 1,000. Additionally, there is a risk that you may faint while having blood collected or having the catheter inserted in your vein.

Muscle Biopsy

During the procedure you may feel discomfort associated with the injection of the numbing drug (the anesthetic) but during the actual muscle removal the discomfort should be minimal. There is a risk that you may faint during the procedure. There is also a risk of muscle cramp, bleeding, of loss of feeling in your leg, and of damage to a skin (cutaneous) nerve. The risk of infection and bruising is extremely small if you follow the instructions for caring for the incision. A very small and minor scar will remain as a result of the incision, but may not be noticeable. These procedures will be performed under surgically clean conditions. Emergency medical equipment will be available. You will be screened prior to the procedure for history of allergic reactions to Novocain (Lidocaine).

5 Radioisotopes/radiation-producing machines(e.g., X-rays, CT scans, fluoroscopy).

Body Composition

The risks associated with the DEXA are very low. The maximum radiation dose you will receive in this study is less than 1/1000th of the federal and state occupational whole body dose limit allowed to radiation workers (5,000 mrem). Put another way, the maximum dose from any scan we utilize with this DEXA ranges from 1.2 mrem (Whole body scan) to 12.2 mrem (for several of the regional scans, such as lumbar, femur, and forearm scans). The average annual background radiation you already receive is at least 620 mrem/year. The more radiation you receive over the course of your life, the more the risk increases of developing a fatal cancer or inducing changes in genes. The radiation in this scan is not expected to significantly increase these risks, but the exact increase in such risks is not known. There are no discomforts associated with this procedure. Women who are or could be pregnant should receive no unnecessary radiation and should not participate in this study.

c)

For the following categories, include an estimate of the potential risk, if applicable.

Protocol Title: Does Dapagliflozin Augment The Favorable Adaptation To Endurance Exercise Training?
Clinical Research Protocol Title: Dapagliflozin Augments The Favorable Adaptation To Endurance Exercise Training

Protocol Type: Biomedical

Date Submitted: 11/01/2018

Approval Period: 11/06/2018-11/05/2019

Important Note: This Print View may not reflect all comments and contingencies for approval. Please check the comments section of the online protocol. Questions that appear to not have been answered may not have been required for this submission. Please see the system application for more details.

1. Physical well-being.

Subjects are provided with the following information pertaining to risks to physical well-being:

Body Composition

The risks associated with the DEXA are very low. The maximum radiation dose you will receive in this study is less than 1/1000th of the federal and state occupational whole body dose limit allowed to radiation workers (5,000 mrem). Put another way, the maximum dose from any scan we utilize with this DEXA ranges from 1.2 mrem (Whole body scan) to 12.2 mrem (for several of the regional scans, such as lumbar, femur, and forearm scans). The average annual background radiation you already receive is at least 620 mrem/year. The more radiation you receive over the course of your life, the more the risk increases of developing a fatal cancer or inducing changes in genes. The radiation in this scan is not expected to significantly increase these risks, but the exact increase in such risks is not known. There are no discomforts associated with this procedure. Women who are or could be pregnant should receive no unnecessary radiation and should not participate in this study.

Exercise Tests and Exercise Training

There is a very small chance of an irregular heartbeat during exercise (< 1% of all subjects). Other rare risks of a stress test are heart attack (< 5 in 10,000) and death (<2 in 10,000). Wearing a mouthpiece and nose-clip can sometimes cause dryness in the mouth and mild discomfort. Difficult exercise may make you feel very tired, light headed and nauseous. Exhausting exercise will, by definition, make you feel very tired. After any exercise your muscles might ache.

Blood Collection

When the needle goes into a vein, it may hurt for a short period of time (a few seconds). Also there may be minor discomfort of having the needle/plastic tube taped to your arm. In about 1 in 10 cases, a small amount of bleeding will occur under the skin that will cause a bruise. The risk of forming a blood clot in the vein is about 1 in 100, and the risk of significant blood loss is 1 in 1,000. Additionally, there is a risk that you may faint while having blood collected or having the catheter inserted in your vein.

Muscle Biopsy

During the procedure you may feel discomfort associated with the injection of the numbing drug (the anesthetic) but during the actual muscle removal the discomfort should be minimal. There is a risk that you may faint during the procedure. There is also a risk of muscle cramp, bleeding, of loss of feeling in your leg, and of damage to a skin (cutaneous) nerve. The risk of infection and bruising is extremely small if you follow the instructions for caring for the incision. A very small and minor scar will remain as a result of the incision, but may not be noticeable. These procedures will be performed under surgically clean conditions. Emergency medical equipment will be available. You will be screened prior to the procedure for history of allergic reactions to Novocain (Lidocaine).

2. Psychological well-being.

Protocol Title: Does Dapagliflozin Augment The Favorable Adaptation To Endurance Exercise Training?
Clinical Research Protocol Title: Dapagliflozin Augments The Favorable Adaptation To Endurance Exercise Training

Protocol Type: Biomedical

Date Submitted: 11/01/2018

Approval Period: 11/06/2018-11/05/2019

Important Note: This Print View may not reflect all comments and contingencies for approval. Please check the comments section of the online protocol.
Questions that appear to not have been answered may not have been required for this submission.
Please see the system application for more details.

N/A

3. **Economic well-being.**

N/A

4. **Social well-being.**

N/A

d) In case of overseas research, or working with a specific race/ethnicity in the United States, provide background on what experience the Investigator(s) have with the proposed population. Describe qualifications/preparations that enable the Investigator(s) to evaluate cultural appropriateness and estimate/minimize risks to subjects.

N/A

e) Special Precautions. Describe the planned procedures for protecting against or minimizing potential risks. If appropriate, include the standards for termination of the participation of the individual subject. Discuss plans for ensuring necessary medical or professional intervention in the event of adverse effects to the subjects.

N/A

f)

Data Safety Monitoring

N Is there a Data Safety Monitoring Board (DSMB)?

If yes, describe its role and indicate who set up the Data Safety Monitoring Board (e.g., sponsor or Protocol Director).

Describe the data and safety monitoring plan developed to ensure the safety of participants and the validity and integrity of research data. Monitoring should be commensurate with risks and with the size and complexity of the trials.

Protocol Title: Does Dapagliflozin Augment The Favorable Adaptation To Endurance Exercise Training?
Clinical Research Protocol Title: Dapagliflozin Augments The Favorable Adaptation To Endurance Exercise Training

Protocol Type: Biomedical

Date Submitted: 11/01/2018

Approval Period: 11/06/2018-11/05/2019

Important Note: This Print View may not reflect all comments and contingencies for approval. Please check the comments section of the online protocol.
Questions that appear to not have been answered may not have been required for this submission.
Please see the system application for more details.

